Cover Page

Title: Improving Social Interaction for Adolescents with Autism During the Transition to Adulthood

NCT Number: NCT03785327

Document Date: 7/2018

Methodology

Participants

In total, we are aiming for 154 participants ages 18 to 21 to be tested interacting in pairs of one autistic and one non-autistic participant. Participants are assigned to one of three conditions:

1. The “neurostimulation” group with 22 autistic and 44 non-autistic adolescents. The autistic participants complete two sessions with different non-autistic participants at least one week apart, once with active neurostimulation preceding the social interaction, and once with sham neurostimulation in order to rule out placebo effects. This group allows for evaluation of Goal 2.
2. The “inclusion training” group with 22 autistic and 22 TD adolescents. Each non-autistic participant receives inclusion training prior to the interaction. Comparing outcomes with the “no intervention” group allows for evaluation of Goal 3.
3. The “no intervention” group consists of 22 autistic and 22 non-autistic adolescents. This group allows for evaluation of Goal 1 and also serves as a baseline for comparison with the intervention groups.

All participants will be male and between 18 and 21 years old. There is a disproportionate male to female ratio in autism of 4:1 (Fombonne, 2009), and the recruitment source used for this study is over 80% male. Thus, we would not have enough female participants to assess gender effects and because social interaction likely differs between mixed-sex interactions relative to same-sex ones, including a handful of females would confound reported findings. All included autistic participants will have a composite score above the clinical threshold for ASD on the Autism Diagnostic Observation Schedule (ADOS-II; Lord et al., 2012). Non-autistic participants will have no history of psychiatric illness or developmental disabilities and no current ASD diagnosis or a first degree relative with an ASD diagnosis. Interaction partners within and across the three groups will be matched on age and race, and comparable on IQ. To control for effects of intellectual ability, and to ensure results are most relevant to autistic older adolescents without intellectual disability, all participants will have measured full-scale IQs over 80 to ensure they are in the average to above average range.

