4. *Friendship Motivation Scale* (Richard & Schneider. 2005): a 12-item questionnaire that assesses the participant's desire to seek out and form social relationships.

Analytic Plan

Sample sizes were selected in consultation with Statistician [name] to ensure successful detection of the anticipated medium effect sizes with 80% power. The research team consists of established researchers who are well experienced in data analysis and interpretation. For this project, we have selected an analytic approach designed to evaluate our three primary research goals. First, all self-report questionnaires will be evaluated for internal consistency using Cronbach's alpha, and the Conversation Probe social behaviors will be evaluated with Intraclass Correlation Coefficients (ICC) for agreement between coders. In addition to reliability, descriptive statistics will be run for all measures, examining group means, standard deviations, and normality of all measures.

Next, all primary goals will be assessed using an "Actor Partner Interdependence Model" (APIM; Kenny, Kashy, and Cook, 2006). Because data will be collected on two interacting individuals, the primary outcomes for both partners will be related (i.e., interaction evaluations, closeness, and impressions are dependent on the interaction with the partner). Thus, outcomes will be non-independent, and traditional analytic techniques using the general linear model cannot be used. Additionally, hypotheses examining how the partners influence each other cannot be examined with these traditional techniques and instead must be modeled with analyses like the APIM that take non-independence into account. APIM can estimate three types of effects. First, APIM can specify actor effects, or the effect of the individual's own behavior (e.g., overall social skills or social cognitive ability) on the individual's own outcome (e.g., interaction quality). Second, these models can specify partner effects, or the effect of the partner's behaviors or abilities on the individual's outcome. Finally, this model can specify interaction effects, allowing for examination of how an individual's behaviors and traits are related to his own outcomes depending on his partner's behaviors and traits.

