To examine effects of autism acceptance training on non-autistic participants interaction with autistic partners, zero-order correlations between participants' interaction ratings were evaluated to assess the relationship between indicators, as well as the consistency of ratings between partners. Two factor mixed-model ANOVAs were run using a Geisser-Greenhouse correction to assess the effects of diagnosis (autistic vs. non-autistic) and training condition (Autism Acceptance Training vs. control) on how participants evaluated their conversation partner and the overall interaction. Specifically, training condition was treated as a between-subjects variable and autistic and NA interaction ratings (interaction quality, first impressions, closeness, warmth and dominance) were treated as a within-subjects factor, with separate analyses run for each outcome measure. As IQ differed significantly between autistic and NA individuals within dyads, WRAT-3 scores were included as a covariate in each ANOVA. All analyses were completed using SPSS 27 (IBM SPSS Inc., 2015).

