All analyses addressing each of the three goals will be conducted separately for each social interaction outcome: social interaction evaluation, closeness, and first impressions formed (i.e., traits and behavioral intentions). Analyses for goal 3 (the “no intervention” condition) will serve as a baseline to compare effectiveness of the neurostimulation intervention (goal 1) and the inclusion training (goal 2). Compared to baseline, it is anticipated that neurostimulation of autistic participants will lead to increased evaluation of their social skill, better performance on social cognitive tasks, and higher ratings by their non-autistic partners on closeness and first impressions. Both partners in the neurostimulation condition are predicted to rate the quality of the social interaction higher than in the baseline condition. Goal 2 (inclusion training for the non-autistic participant) is predicted to lead to higher ratings of closeness and first impressions made by non-autistic participants of their autistic partners, with both partners evaluating the social interaction more positively compared to the “no intervention” condition. Because inclusion training only targets the non-autistic individual, social skill and social cognitive performance of autistic participants is not expected to differ here compared to baseline. Finally, we will be able to compare effects between Goal 1 and Goal 2 to determine which intervention, neurostimulation or inclusion training, produces better social outcomes for autistic adolescents. Due to the number of tests that will be performed, all significance tests will be evaluated at an adjusted alpha threshold of .01.

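### The stated 80% power for medium effects is not supported for the between-group comparisons: at the plan's alpha of .01, 22 against 22 dyads gives about 16% for one partner's rating and 23–37% if both partners shift

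*Combined protocol and SAP*

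**What the plan says.** The opening of the Analytic Plan gives the only justification for the sample size: it was chosen "to ensure successful detection of the anticipated medium effect sizes with 80% power". No number is attached to medium, and no test, alpha, sidedness or correlation is given.

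The last paragraph of that section states that, because many tests are planned, "all significance tests will be evaluated at an adjusted alpha threshold of .01".

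The Participants section fixes the group sizes. The inclusion-training arm is a "group with 22 autistic and 22 TD adolescents", and the comparison arm, the no-intervention "group consists of 22 autistic and 22 non-autistic adolescents". In the neurostimulation arm there are 22 autistic and 44 non-autistic participants: "The autistic participants complete two sessions with different non-autistic participants at least one week apart", one session active and one sham. The total of 154 is consistent with this (22 + 44 + 22 + 22 + 22 + 22).

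The last paragraph of the Analytic Plan predicts differences from the no-intervention group. For inclusion training it expects the non-autistic partner's closeness and first-impression ratings to rise, "with both partners evaluating the social interaction more positively compared to the" no-intervention condition. For the autistic partners in that arm it expects no effect: "social skill and social cognitive performance of autistic participants is not expected to differ here compared to baseline". The paragraph on the training analysis treats condition as a between-subjects factor and states that "WRAT-3 scores were included as a covariate in each ANOVA".

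**The concern.** Twenty-two independent dyads per group is a small sample for a medium standardised difference, and an alpha of .01 makes it harder still. The power claim is general, yet the comparisons that evaluate inclusion training, and neurostimulation against no intervention, are of this 22-against-22 kind. If the claim fails there, a reader will treat a non-significant group difference as informative when the study was unlikely to detect the effect it was planned around.

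The risk is sharper because one prediction is an absence of change. If inclusion training did change an autistic participant's social skill or social cognition score by d = 0.5, a test with 16% power would miss it about 84% of the time, and the result would look like confirmation. The plan has no rule that reads non-significance as no effect, but nothing in it prevents that reading.

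**Working it through.** **Inputs from the documents.** 22 dyads per comparison group and 22 autistic participants with two sessions each (Participants); alpha .01 for all tests and a target power of 80% (Analytic Plan).

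**Assumptions not in the documents.** Medium is d = 0.5, or f = .25 for ANOVA terms; tests are two-sided; data are complete, which favours the plan. Correlations between partners and between sessions are not given, so ranges are shown. All power figures use the noncentral t distribution.

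**The plan's own figure.** The 80% cannot be reproduced from stated inputs, because none are stated. The cases below test whether a reasonable choice of inputs recovers it.

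**1. One partner's rating, 22 against 22.** df = 42; noncentrality = d × √(22/2) = 0.5 × √11 = 1.658. The two-sided critical value is 2.698 at .01 and 2.018 at .05.
- Power is 16.3% at .01 and 36.7% at .05 (one-sided: 23.5% and 49.5%).
- 80% power at d = 0.5 needs 96 dyads per group at .01, or 64 at .05.
- With 22 per group, the effect detectable with 80% power at .01 is d ≈ 1.07.

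**2. Both partners shift by 0.5 SD, tested on the dyad mean.** Effective d = 0.5/√((1 + r)/2), where r is the correlation between partners.

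| r | effective d | power at .01 | power at .05 |
|---|---|---|---|
| 0 | 0.707 | 37% | 63% |
| .3 | 0.620 | 27% | 52% |
| .5 | 0.577 | 23% | 46% |

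The shift in both partners detectable with 80% power at .01 is 1.074 × √((1 + r)/2): 0.76 SD at r = 0 and 0.93 SD at r = .5. One-sided testing at .05 with r = 0, the most favourable version without a covariate, gives 75%.

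**3. Covariate adjustment.** d is divided by √(1 − ρ²), with df = 41. A covariate correlating .5 with the outcome raises case 1 at .01 from 16% to 23%, and case 2 at .01 with r = 0 from 37% to 51%. For one partner's rating to reach 80% at .01, the correlation would have to lie between .88 (78%) and .89 (82%).

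**4. Active against sham, 22 pairs.** df = 21; dz = 0.5/√(2(1 − r)), where r is the correlation between sessions.

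| r | dz | power at .01 | power at .05 |
|---|---|---|---|
| 0 | 0.354 | 15% | 35% |
| .3 | 0.423 | 23% | 47% |
| .5 | 0.500 | 34% | 61% |
| .6 | 0.559 | 44% | 71% |
| .7 | 0.645 | 58% | 82% |
| .8 | 0.791 | 80% | 94% |

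The detectable dz at 80% power and .01 is about 0.79. The partner changes between sessions, so a correlation near .8 is more plausible for the autistic participant's own scores than for partner ratings. That is a judgement, not a figure from the plan.

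**5. Role-by-condition interaction.** This is tested on the within-dyad difference, with SD √(2(1 − r)). In a 2 × 2 layout f = .25 puts each cell's interaction term at ±0.25 SD, so the difference in differences is 4 × 0.25 = 1.0 SD.
- For that effect, power at .01 is 73% at r = .5 and 84% at r = .6 (90% and 95% at .05).
- If only one partner shifts by 0.5 SD, the same test has 16% and 21% at .01.

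**6. The predicted absence of change.** The chance of non-significance when d is truly 0.5 is 1 − 0.163 = 0.837 for one test. For three independent measures all to be non-significant it is 0.837³ = 0.586.

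**The case against.** The strongest reply is that the 80% is not tied to any test, so the choice of a two-group contrast with d = 0.5 is the critic's. The training analysis is a two-factor mixed ANOVA. If medium is read as f = .25, the role-by-condition term has 78% power at .05 with a partner correlation of .3, and about 80% at .01 with a correlation of about .57. Extended to three conditions and 66 dyads, it has 85% at .01 with a correlation of .5. The interaction pattern is also predicted: the Measures section expects training to improve non-autistic impressions without altering autistic responses. In addition, the stated primary model is an actor–partner model, whose actor and partner effects are not evaluated here.

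This does limit the point. A conventional calculation can give about 80% for one term, and the documents do not show which calculation was run. It does not rescue the general claim. The f = .25 route needs a 1.0 SD difference in differences, and the plan states no magnitude that large. It also does not target the prediction that both partners rate the interaction higher. The t-based tests are reasonable proxies for a condition effect in a dyadic model; power for actor and partner effects of traits is a separate question, left open.

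Two smaller objections stand. The 59% for three measures assumes independence; measures from the same participants would be correlated, and simulated values were about 63% to 71% for correlations of .3 to .7, so independence understates this risk. Also, part of the analysis is described in the past tense, so a corrected statement may follow some results. It should then be labelled as a restatement from the planned sizes.

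**Conclusion.** The concern holds. For the predicted differences between each intervention group and the no-intervention group, the 80% claim is unsupported at the plan's own alpha: 16% for one partner's rating and 23% to 37% for both. These figures rest on d = 0.5, two-sided tests, complete data and a partner correlation between 0 and .5. The conclusion is not sensitive to the main choices: relaxing alpha to .05, testing one-sided, or both, still leaves every version without a covariate below 80%, and reading medium as d = 0.8 gives only 49% for one partner at .01. Covariate adjustment would rescue the one-partner comparison at .01 only with a correlation of about .88 to .89.

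Two routes to 80% at .01 exist, active against sham with a session correlation of about .8 and the interaction at f = .25, but each needs an input the plan does not state. Because the plan's only sample-size justification fails for these comparisons, it should be corrected and not left as it is.

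**What to change.** First recover the inputs behind the 80% figure (test, effect-size metric, alpha, sidedness, assumed correlations) and state them at the start of the Analytic Plan. Then restate power at .01 using them.

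If they cannot be recovered, wording such as this would serve:

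> With 22 dyads per group and two-sided alpha .01, the study has 80% power for d of about 1.07 between groups (one partner's rating) and dz of about 0.79 for active against sham. For d = 0.5, power is about 16% between groups, or 23% to 37% if both partners shift and are analysed jointly (partner correlation .5 to 0). For active against sham it runs from 15% to 80% as the session correlation goes from 0 to .8. These figures assume complete data.

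A reporting sentence is a useful addition:

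> Non-significant results, including the expected lack of change in autistic social skill and social cognition under inclusion training, will be reported as estimates with confidence intervals and not read as no effect.

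The cost is wording only: no extra participants and no change of design. The stated power becomes less favourable.

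### The plan assigns every goal to the APIM but tests training by mixed ANOVA, and ties no test to the predicted gain in non-autistic participants' ratings

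*Combined protocol and SAP*

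**What the plan says.** The APIM paragraph of the Analytic Plan states that "all primary goals will be assessed using an" APIM. Because partners' outcomes are related, it adds that "traditional analytic techniques using the general linear model cannot be used". It describes actor, partner and interaction effects of behaviours, abilities and traits. Training condition is not listed as a term.

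The paragraph on training describes a different model: "Two factor mixed-model ANOVAs were run using a Geisser-Greenhouse correction to assess the effects of diagnosis" and "training condition (Autism Acceptance Training vs. control"). Training is the between factor. The ratings given by the autistic and non-autistic partners "were treated as a within-subjects factor, with separate analyses run for each outcome measure". No interaction and no contrast within one type of rater is named. The same paragraph says: "As IQ differed significantly between autistic and NA individuals within dyads, WRAT-3 scores were included as a covariate in each ANOVA". The Participants section had planned partners "matched on age and race, and comparable on IQ".

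The predictions stand elsewhere. The closing paragraph of the Analytic Plan expects training to raise closeness and first-impression ratings given by non-autistic participants, and expects both partners to evaluate the interaction more favourably. It sets alpha at .01. The Measures section expects training to improve non-autistic impressions and to leave autistic responses unchanged. Under Participants, the training group is described so: "Each non-autistic participant receives inclusion training prior to the interaction". That group and the no-intervention group have 22 dyads each.

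**The concern.** Two models are given for the training goal, one of which the plan itself says cannot be used, and nothing ranks them. Nor does either model, as written, contain the test that the hypothesis calls for. For closeness and first impressions the question is whether non-autistic raters score their partners higher after training. The ANOVA offers a training effect averaged over both raters and, by convention, an interaction that is the difference between raters.

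These effects can give different answers on the same data. If only non-autistic ratings rise, the main effect is diluted. If autistic ratings rise too, the interaction shrinks although the predicted gain is real. Cell means would show which partner moved, but no named test decides the goal. The .01 threshold limits false positives; it does not settle which contrast is tested.

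**Working it through.** **The plan's own figure.** The Analytic Plan claims 80% power for medium effects. It does not give the effect metric, the test or the within-dyad correlation, so the figure cannot be reproduced uniquely. Reading medium as 0.5 SD, a two-sample t test with 22 per group has 37% power at two-sided .05 and 16% at two-sided .01.

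**Inputs.** From the documents: 22 dyads per group and alpha .01. Assumed: the ANOVA's two conditions are inclusion training and no intervention; tests are two-sided; rating SDs are equal in both roles; partner correlation r is 0 to .5; there is no covariate.

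**Formulas.** Let dN and dA be the training shifts in non-autistic and autistic ratings, in SD units. The standardised effects are:

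- direct contrast among non-autistic raters: dN
- main effect (dyad mean): (dN + dA) / √(2 + 2r)
- interaction (dyad difference): (dN − dA) / √(2 − 2r)

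Power is from the noncentral t with 42 degrees of freedom and noncentrality equal to the effect × √(22/2).

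**Worked case, dN = 0.5, dA = 0.** Direct: 0.5 × √11 = 1.658, power 16.3%. At r = 0, main effect and interaction are both 0.5/√2 = 0.354, power 7.4%. At r = .5, the main effect is 0.5/√3 = 0.289, power 4.9%; the interaction is 0.5/√1 = 0.5, power 16.3%.

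| dN | dA | Direct | Main effect, r = 0 / .3 / .5 | Interaction, r = 0 / .3 / .5 |
|---|---|---|---|---|
| 0.5 | 0 | 16.3% | 7.4 / 5.6 / 4.9% | 7.4 / 11.0 / 16.3% |
| 0.8 | 0 | 48.9% | 22.0 / 16.0 / 13.5% | 22.0 / 33.7 / 48.9% |
| 0.8 | 0.4 | 48.9% | 55.1 / 41.9 / 35.6% | 4.7 / 6.7 / 9.7% |
| 0.8 | 0.8 | 48.9% | 84.8 / 72.1 / 64.3% | 1.0% throughout |

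The last interaction entry is simply alpha: when both raters gain equally, the interaction is zero.

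**Reading the table.** With dA = 0 and r not negative, the main effect's divisor is at least √2, so it cannot beat the direct contrast. It can when autistic ratings also rise: 55% against 49% in the third row at r = 0. The main effect also cannot tell who moved. If only autistic ratings rise by 0.8 SD, it is significant in the predicted direction in 22% to 13% of trials, with no gain among non-autistic raters.

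**Unequal SDs.** Let k be the autistic SD divided by the non-autistic SD. The divisors become √(1 + k² ± 2rk), with plus for the main effect. At dN = 0.8, dA = 0 and k from 0.7 to 1.5, power is 8% to 31% for the main effect and 12% to 61% for the interaction. The interaction beats the direct contrast only if k < 2r.

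**Pairing.** In 20,000 simulated null trials at each of r = 0, .3 and .6, main-effect and interaction tests with the dyad as unit rejected 0.9% to 1.2% of the time at nominal 1%.

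**The case against.** The plan excludes general linear models because of non-independence, and an ANOVA with rater as a within-dyad factor deals with that. A reader might infer that the ANOVA ignores the pairing and has false error rates; the layout described and the simulation do not support this. The APIM and the ANOVA could also be read as serving different questions, since the APIM text never lists training. That reading does not settle the matter, because the APIM is assigned to all primary goals.

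A two-factor ANOVA conventionally includes the interaction, and the Measures section predicts no change in autistic responses. Under that prediction the interaction is a legitimate test for first impressions, with power equal to the direct contrast at r = .5 and equal SDs. This stands, but the equivalence in expectation holds only if autistic ratings do not change. The closing paragraph itself predicts that they improve for interaction evaluation.

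A reader might also infer that the plan never names an effect in non-autistic raters. It does, as a hypothesis in both Measures and the Analytic Plan; what is missing is the test. Nor do the documents show that the ANOVA was chosen after data were seen. The past tense is suggestive, but only the covariate is given a reason that comes from observed data.

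Finally, at 0.5 SD every candidate test has low power, so naming the contrast gains little sensitivity. That is correct.

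**Conclusion.** The point holds as an unreconciled conflict between two models and a missing link from hypothesis to test. It is not a finding of invalid error control. For closeness and first impressions, the answer on training depends on which effect is read, and the plan does not say. At 0.5 SD in non-autistic raters alone, choosing the main effect over the direct contrast cuts power from 16% to between 7% and 5%. At 0.8 SD the fall is from 49% to between 22% and 13%. The interaction ranges from matching the direct contrast to 1% power, depending on r and on whether autistic ratings also rise. These sizes rest on the assumptions listed in the working, none of which the documents confirm. The plan should be corrected, but the matter can be settled by wording and re-analysis.

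**What to change.** - **Model.** Reconcile the APIM and ANOVA paragraphs. Name one distinguishable-dyad role-by-condition model as primary and call the other supportive.
- **Closeness and first impressions.** Make training against no intervention among non-autistic raters the deciding contrast. Keep the autistic-rater contrast and the interaction as secondary.
- **Interaction evaluation.** Report the training contrast in each role, and claim that both partners improved only if both contrasts support it. The averaged effect may serve as an overall summary.
- **Consistency.** Reconcile the Measures prediction of no effect on autistic responses with the Analytic Plan prediction that both partners improve. State the status of warmth and dominance, which appear in the ANOVA paragraph. State whether Autism Acceptance Training against control is inclusion training against no intervention.
- **Timing.** Label the re-specified contrasts as retrospective if they were set after data were seen.
- **Separate minor point.** Label the WRAT-3 covariate as prompted by the data, and report results with and without it.

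The cost is revised wording and re-analysis, with no new participants. The downside is that the ANOVA becomes supportive, the deciding contrast may be post hoc, and power stays low. The change clarifies the question tested; it does not cure the sample size.

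### The Analytic Plan contains no active-versus-sham test and judges neurostimulation against the no-intervention group, so a placebo or set-up effect could be reported as efficacy

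*Combined protocol and SAP*

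**What the plan says.** **Participants section, neurostimulation group.** This is a "group with 22 autistic and 44 non-autistic adolescents". On the sessions: "The autistic participants complete two sessions with different non-autistic participants at least one week apart". One of the two visits is active; the control visit is described as "once with sham neurostimulation in order to rule out placebo effects". The section then says that this group is the one used to evaluate the neurostimulation goal.

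**Participants section, no-intervention group.** "This group allows for evaluation of Goal 1 and also serves as a baseline for comparison with the intervention groups".

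**Analytic Plan.** The primary model is an APIM described in general terms (actor, partner and interaction effects), with no term for session, stimulation or order. The ANOVA paragraph covers only the training comparison. The final paragraph says that the no-intervention analyses "will serve as a baseline to compare effectiveness of the neurostimulation intervention (goal 1) and the inclusion training (goal 2"). It states the neurostimulation hypotheses against that baseline, for example: "Both partners in the neurostimulation condition are predicted to rate the quality of the social interaction higher than in the baseline condition". The only other neurostimulation contrast named is the one against inclusion training. Sham is not mentioned anywhere in the Analytic Plan. All tests use alpha .01, and sidedness is not stated.

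The goal numbers differ between sections. Neurostimulation is Goal 2 in the Participants section and goal 1 in the final paragraph of the Analytic Plan. This needs reconciling but does not affect the argument.

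**The concern.** The design pays for a placebo control: 22 sham sessions and a second set of 22 partners. The analysis that would use it is not written down. The comparator that is written down received no stimulation procedure at all, so it cannot separate the effect of stimulation from the effect of being set up for stimulation and expecting a benefit.

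Exposure differs by outcome. It is most direct for what the autistic participant reports or performs, such as interaction quality ratings and social cognitive tasks. It is indirect for closeness and first impressions rated by the partner, who receives no stimulation.

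Two further gaps affect what is estimated. The plan does not say whether the active session, the sham session or both represent the neurostimulation condition. The order of the two sessions is also unstated.

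**Working it through.** **What each comparison estimates.** Let S be the stimulation effect, P the placebo or set-up effect, and G any difference between groups made up of different people.

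| Comparison | Estimates |
|---|---|
| Active session vs no intervention | S + P + G |
| Both sessions averaged vs no intervention | ((S + P) + P)/2 + G = S/2 + P + G |
| Active vs sham, same participant | S (plus an order effect if order is unbalanced and unmodelled) |

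Only the third isolates S, and it is the one the Analytic Plan omits. With S = 0.5 SD and P = G = 0, averaging the sessions would estimate 0.25 SD instead of 0.5.

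**Inputs.** From the documents: 22 dyads in the no-intervention group, 22 autistic participants with two sessions each, alpha .01. Assumed, because no value is given: two-sided tests, a simple t-test in place of the APIM, the size of P, the within-person correlation ρ, and d = 0.5 for a medium effect. The stated 80% power cannot be reproduced, since no numeric effect size, correlation or test is given. The concern does not rest on it.

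**False efficacy when S = 0 and G = 0.** The statistic is noncentral t with df = 42 and noncentrality P × √(22/2) = 3.317 P.

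| Assumed P (SD) | Noncentrality | Significant, either direction (nominal 1%) | Significant in favour of neurostimulation (nominal 0.5%) |
|---|---|---|---|
| 0.2 | 0.663 | 2.70% | 2.63% |
| 0.3 | 0.995 | 5.29% | 5.27% |
| 0.5 | 1.658 | 16.30% | 16.30% |

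These are per outcome. In every row the estimate is biased by the whole of P.

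**Power of the omitted contrast.** For 22 pairs, dz = 0.5/√(2(1 − ρ)) and the noncentrality is dz × √22.

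| ρ | dz | Power, df 21 | Power, df 20 (balanced order term) |
|---|---|---|---|
| 0 | 0.354 | 14.8% | 14.7% |
| 0.1 | 0.373 | 16.8% | 16.6% |
| 0.3 | 0.423 | 22.7% | 22.5% |
| 0.5 | 0.500 | 34.0% | 33.6% |

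The between-group test of 22 vs 22 at d = 0.5 has 16.3%. The paired test matches it at ρ = 0.078 (df 21) or 0.085 (df 20) and exceeds it above that. For partner-rated outcomes ρ may be near 0 to 0.1, because a different partner does the rating in each session.

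**Session order.** If k of 22 participants receive active second and the second session carries an effect g, active minus sham without an order term is biased by g(2k − 22)/22. With g = 0.2 SD (assumed):

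- k = 22: 0.2 × 22/22 = 0.20 SD
- k = 14: 0.2 × 6/22 = 0.05 SD
- k = 11: 0

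At k = 22 order and stimulation coincide, so no model term can separate them.

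**The case against.** The Participants section does more than hint at the sham contrast. It says that sham is there to exclude placebo effects and ties evaluation of the neurostimulation goal to the group holding both sessions. For inclusion training, by contrast, it explicitly names the comparison with no intervention. The Analytic Plan is a short narrative that spells out model terms for no goal, and silence about sham does not exclude it. On this reading the plan only under-specifies an intended analysis. The natural reading is also that the neurostimulation condition means the active session; nothing suggests averaging in sham. Groups are to be matched on age and race and comparable on IQ. The placebo and practice effects used above are assumptions, and at 0.2 to 0.3 SD the inflation is modest.

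**What stands.** The intent is real, and the defect lies in the analysis specification, not the design. The averaging and order figures illustrate what is left open; they do not describe a plan anyone wrote. The placebo sizes are assumptions.

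**What does not.** Intent supplies no contrast, model term or priority among tests. The same section also says that the no-intervention group "also serves as a baseline for comparison with the intervention groups", and that is the only role carried into the Analytic Plan. A comparator is therefore stated, and it is one that leaves placebo in the estimate. Matching on age, race and IQ does nothing about that.

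**Conclusion.** The concern holds, and the plan must be corrected on this point. The textual finding needs no assumption: the Analytic Plan has no active-versus-sham test, and the named comparator for neurostimulation effectiveness is the no-intervention group. The bias equals the full placebo or set-up effect plus any group difference, and it carries into the ranking against inclusion training.

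How often this would yield a false claim depends on a placebo size the documents do not give; the range shown covers 0.2 to 0.5 SD under the t-test approximation. Exposure is greatest for outcomes the autistic participant reports or performs. The argument for the sham contrast is validity. A gain in power is likely only where the within-person correlation is clearly above about 0.08 to 0.09. The missing statement of session order would, taken alone, be only a missing detail.

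**What to change.** In the final paragraph of the Analytic Plan:

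1. Make the within-participant active-versus-sham contrast the primary neurostimulation test for each outcome. A suitable model has a random intercept for the autistic participant, a fixed term for session order, and a separate dyad (partner) covariance for each session, because the partner changes.
2. State how session order is assigned. If it is the same for everyone, say so and acknowledge that order cannot be separated from stimulation.
3. Keep the comparison with no intervention as secondary, state that it uses the active session, and label it not placebo-controlled.
4. Report active minus sham alongside any ranking of neurostimulation against inclusion training.

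**Cost.** Revised wording and one extra contrast per outcome on data already planned for collection, with no new participants or visits. The reported effect may be smaller once placebo is removed. Where the within-person correlation is near 0 to 0.1, power is about the same as for the between-group test (15 to 17% against 16% at d = 0.5).
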